6.19.5.1. Abnormal Hepatic Tests

Analyses for abnormal hepatic tests involve 4 laboratory analytes: ALT, AST, total bilirubin, and ALP. Analyses for the change from baseline to last visit that occurred on or before the date of treatment discontinuation and shift tables are described in Section 6.19.5. This section describes additional analyses for the topic. The central laboratory reference ranges (Covance) will be used for ALT, AST, total bilirubin, and ALP hepatic laboratory assessments.

The number and percentage of patients with the following abnormal elevations in hepatic laboratory tests at any time up to 60 days after treatment discontinuation will be summarized by treatment group. LY3471851 groups will be compared to placebo using Fisher's exact test:

- The percentages of patients with an ALT measurement $\geq 3\times$, $5\times$, and $10\times$ the central laboratory ULN during the treatment and follow-up periods will be summarized for all patients with a postbaseline value and for subsets based on various levels of baseline.
 - The analysis of $3\times$ ULN will contain 4 subsets: patients whose nonmissing maximum baseline value is $\leq 1\times$ ULN; patients whose maximum baseline is $>1\times$ ULN, but $<3\times$ ULN; patients whose maximum baseline value is $\geq 3\times$ ULN; and patients whose baseline values are missing.
 - The analysis of $5\times$ ULN will contain 5 subsets: patients whose nonmissing maximum baseline value is $\leq 1\times$ ULN; patients whose maximum baseline is $>1\times$ ULN, but $<3\times$ ULN; patients whose maximum baseline is $\geq 3\times$ ULN, but $<5\times$ ULN; patients whose maximum baseline value is $\geq 5\times$ ULN; and patients whose baseline values are missing.
 - The analysis of $10\times$ ULN will contain 6 subsets: patients whose nonmissing maximum baseline value is $\leq 1\times$ ULN; patients whose maximum baseline is $>1\times$ ULN, but $<3\times$ ULN; patients whose maximum baseline is $\geq 3\times$ ULN, but $<5\times$ ULN; patients whose maximum baseline is $\geq 5\times$ ULN, but $<10\times$ ULN; patients whose maximum baseline value is $\geq 10\times$ ULN; and patients whose baseline values are missing.
- The percentages of patients with an AST measurement greater than or equal to $3\times$, $5\times$, and $10\times$ the central laboratory ULN during the treatment and follow-up periods will be summarized for all patients with a postbaseline value and for subsets based on various levels of baseline. Analyses will be constructed as described above for ALT.
- The percentages of patients with a total bilirubin measurement greater than or equal to $2\times$ the central laboratory ULN during the treatment period will be summarized for all patients with a postbaseline value and subset into 4 subsets: patients whose nonmissing maximum baseline value is $\leq 1\times$ ULN; patients whose maximum baseline is $>1\times$ ULN but $<2\times$ ULN; patients whose maximum baseline value is $\geq 2\times$ ULN; and patients whose baseline values are missing.
- The percentages of patients with an ALP measurement $\geq 1.5\times$ the central laboratory ULN during the treatment and follow-up periods will be summarized for all patients with a postbaseline value and subset into 4 subsets: patients whose nonmissing maximum baseline value is $\leq 1\times$ ULN; patients whose maximum baseline is $>1\times$ ULN but $<1.5\times$ ULN; patients whose maximum baseline value is $\geq 1.5\times$ ULN; and patients whose baseline values are missing.

Second, to further evaluate potential hepatotoxicity, an eDISH plot will be created for all patients whether treated with LY3471851 and/or other treatment using the whole study and follow-up periods. Each patient with at least 1 postbaseline ALT and total bilirubin will be included in the eDISH. The points correspond to maximum total bilirubin and maximum ALT, even if not

obtained from the same blood draw. A listing of patients potentially meeting Hy's rule will be provided (defined as greater than or equal to $3 \times$ ULN for ALT or AST, and greater than or equal to $2 \times$ ULN for total bilirubin, not necessarily at the same time).

Third, a listing will be provided to the medical safety team for internal review according to the following SMQs:

- broad and narrow terms in the Liver-related investigations, signs and symptoms SMQ (SMQ 20000008)
- broad and narrow terms in the Cholestasis and jaundice of hepatic origin SMQ (SMQ 20000009)
- broad and narrow terms in the Hepatitis non-infectious SMQ (SMQ 20000010)
- broad and narrow terms in the Hepatic failure, fibrosis and cirrhosis and other liver damage-related conditions SMQ (SMQ 20000013), and
- narrow terms in the Liver-related coagulation and bleeding disturbances SMQ (SMQ 20000015)

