2.3. Benefit/Risk Assessment

The Investigator's Brochure (IB) designates local injection site reactions (ISR) as an identified risk of LY3471851, based on reports of primarily low-grade injection site reactions in the Phase 1 studies. Reports of cytokine release syndrome (CRS) and clinical symptom complex attributed to elevated cytokine levels were of Grade 1 severity. Eosinophilia without evidence of target organ damage was observed in some participants in the Phase 1 study in SLE. The safety findings from Phase 1 studies showed no evidence of adverse events characteristic of capillary leak syndrome, increased risk of infection, worsening or new onset autoimmune disease, cardiac disorders (cardiac rhythm disturbances, angina, or myocardial infarction), pulmonary disorders, central nervous system effects, or severe anemia/thrombocytopenia known to be associated with high-dose IL-2 (aldesleukin).

To minimize study participant risk in Study KFAJ, enrolled participants will receive study drug doses in the clinic to enable appropriate pre-dose safety assessments and post-dose monitoring. The routine safety assessments include physical examinations, clinical safety laboratory tests (including hematology and chemistry), suicidality/self-harm and depression evaluations, and collection of vital signs and spontaneously reported adverse events. The study design includes a post-treatment follow-up period with at least one study visit for safety assessments.

CCI

In addition, based on observations of treatment-related biliary hyperplasia noted in nonclinical studies, as described in the IB, investigators should be aware of the possible occurrence of treatment-related hepatobiliary changes that could possibly include cholestasis. The protocol includes hepatic-related laboratory testing to support intensive monitoring for symptoms and physical signs suggestive of liver or biliary toxicity, including jaundice, scleral icterus, and pruritis. See also Section 8.2.9.

Ongoing study-level monitoring of safety data will be performed, as described in Section 8.2.

CCI

The efficacy of LY3471851 in SLE has not been established. Participants may benefit by receiving personal health information from the physical examinations and from other routine safety assessments performed in this study.

In summary, in the context of the cumulative knowledge for LY3471851, the benefit/risk balance for this study is assessed to be acceptable for testing in Phase 2.

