Hepatic event or liver test abnormality

- Participants who are discontinued from study drug because of a hepatic event or liver test abnormality should have additional hepatic safety data collected via the hepatic eCRF packet. Discontinuation of study drug because of abnormal liver tests should be considered by the investigator when a participant meets one of the following conditions after consultation with the sponsor's designated medical monitor (see Section 8.2.9).
 - ALT or AST >8 times ULN
 - ALT or AST >5 times ULN sustained for more than 2 weeks
 - ALT or AST >3 times ULN and TBL >2 times ULN or international normalized ratio (INR) >1.5
 - ALT or AST >3 times ULN with the appearance of fatigue, nausea, vomiting, right upper-quadrant pain or tenderness, fever, rash, and/or eosinophilia ($>5\%$)
 - alkaline phosphatase (ALP) >3 times ULN
 - ALP >2.5 times ULN and TBL >2 times ULN, or
 - ALP >2.5 times ULN with the appearance of fatigue, nausea, vomiting, right upper quadrant pain or tenderness, fever, rash, and/or eosinophilia ($>5\%$).

Other reasons

- Unblinding: If an investigator, blinded site personnel who are performing assessments, or participant is unblinded to a participant's treatment assignment, the participant must be discontinued from the study drug and continue to post-treatment follow-up. In cases where there are ethical reasons to have the participant continue on study drug, the investigator must obtain specific approval from the sponsor's designated medical monitor for the participant to continue.

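### In the SAP's liver tables the bilirubin bullet contradicts its own lead-in on the follow-up window, and ALP is neither graded above 1.5x ULN nor combined with bilirubin (minor)

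*SAP*

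**What the plan says.** SAP 6.19.5.1 introduces its liver-test tables with a common window: "abnormal elevations in hepatic laboratory tests at any time up to 60 days after treatment discontinuation will be summarized by treatment group". Four bullets follow.

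- **ALT and AST:** at least 3x, 5x and 10x ULN, over treatment and follow-up.
- **Total bilirubin:** at least 2x ULN, restricted in time by the words "the central laboratory ULN during the treatment period will be summarized for all patients with a postbaseline value".
- **ALP:** a single cut-off of at least 1.5x ULN, with the wider window: "the central laboratory ULN during the treatment and follow-up periods will be summarized for all patients with a postbaseline value and subset into 4 subsets".

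The same section adds an eDISH plot of maximum ALT against maximum bilirubin, a listing of potential Hy's rule cases (ALT or AST with bilirubin), and SMQ-based listings for internal medical review.

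Protocol 2.3 reports biliary hyperplasia in nonclinical studies and alerts investigators to the "possible occurrence of treatment-related hepatobiliary changes that could possibly include cholestasis". Among the liver criteria for considering discontinuation, Protocol 7.1.1 lists "alkaline phosphatase (ALP) >3 times ULN", as well as ALP above 2.5x ULN together with bilirubin above 2x ULN.

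**The concern.** The lead-in and the bilirubin bullet give a programmer two incompatible windows for the same table, and the SAP gives no reason for treating bilirubin differently from the other three tests. If the bullet is followed, a participant whose bilirubin first reaches 2x ULN at the post-treatment visit is absent from the by-arm count at that level, while an ALT, AST or ALP elevation found in the same blood sample is counted.

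The ALP question is about resolution. The protocol's stated liver concern is hepatobiliary, yet the tests graded at three levels are ALT and AST. With one ALP cut-off and no joint ALP-bilirubin category, the by-arm rates cannot separate a mild ALP rise from one that reaches a level on which the protocol acts. The study is meant to guide dose selection and characterize benefit and risk (Protocol 2.1), so a dose-related pattern of this kind should be readable from the tables.

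**Working it through.** The plan gives no figure to reproduce here. The check compares windows and cut-offs, then counts visits.

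**1. Windows and cut-offs in SAP 6.19.5.1**

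| Item | Window | Cut-offs (x ULN) |
|---|---|---|
| Lead-in | to 60 days after discontinuation | all listed tests |
| ALT | treatment and follow-up | 3, 5, 10 |
| AST | treatment and follow-up | 3, 5, 10 |
| Total bilirubin | treatment only | 2 |
| ALP | treatment and follow-up | 1.5 |

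Bilirubin is the only row that departs from the lead-in.

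**2. Where Visit 801 falls for a completer.** Inputs are from Protocol 1.3 (Schedule of Activities): last dose at Week 22 (Day 155), Visit 15 on Day 169, Visit 801 on Day 211 with a 7-day tolerance. SAP 6.4 ends a completer's treatment period at Visit 15.

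- From last dose: 211 - 155 = 56 days. From Visit 15: 211 - 169 = 42 days.
- Both are within 60 days, so the lead-in includes Visit 801 and the bilirubin bullet excludes it.
- At the late end of the tolerance (Day 218) the gaps are 63 and 49 days. The visit then passes 60 days only if the count starts at the last dose.

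**3. How much the narrow reading drops for a completer.** Post-baseline chemistry is scheduled at Visits 3 to 9, 11, 13 and 15, which is 10 draws. Visit 801 makes 11.

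- Draws lost: 1/11 = 9%.
- Days lost: (211 - 169)/(211 - 1) = 42/210 = 20%.

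Visit 802 (Day 267, and 267 - 169 = 98 days after Visit 15) does not enter the comparison. It lies beyond 60 days, and SAP 6.4 limits safety analyses of follow-up to the first follow-up visit.

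**4. Early discontinuers.** SAP 6.4 extends their treatment period to an early termination visit less than 42 days after stopping or, if that visit is later, to the last visit within that limit. Some post-stopping bilirubin is therefore already counted, and mainly Visit 801 is lost.

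**5. Does the 1.5x ALP cut-off miss anyone?** The protocol's ALP levels are at least 2x ULN (8.2.9 and 8.2.9.1), above 2.5x with bilirubin above 2x or with symptoms (7.1.1), at least 3x (8.2.9) and above 3x (7.1.1). Each lies above 1.5x, so each group is a subset of the tabulated one. The baseline-relative rule in 8.2.9 is also covered: at least 2x a baseline of at least 1.5x ULN means at least 2 x 1.5 = 3x ULN. No such patient is missed; only the split by severity is absent.

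**6. Where else such findings appear**

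- *Treatment-emergent high (SAP 6.19.5):* by arm and to 60 days, but at the reference limit, and only for patients at or below that limit at all baseline visits. Exclusion criterion 43 admits bilirubin below 1.5x ULN and sets no ALP limit, so some enrolled patients may not qualify for this table.
- *Box plots and abnormal-findings listing (SAP 6.19.5):* the plots include the first follow-up visit and mark out-of-range values. Neither output gives a rate at 2x ULN.
- *eDISH:* covers the whole study and follow-up, including bilirubin, but has no ALP axis.
- *Cholestasis and jaundice SMQ:* a listing of coded events, not a laboratory rate.
- *Shift tables:* 6.19.5.1 refers to 6.19.5 for these, but the readable text there describes none. Appendix 6 only marks ALP and bilirubin for outlier/shift analysis.

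**The case against.** The strongest reply is that this section is supplementary and the plan looks for liver effects in several other places. That is correct, and it defeats two stronger readings that a reader might infer.

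- *That the tables can miss cholestasis because ALP is counted only at 1.5x ULN.* The direction is wrong. A lower cut-off is more inclusive, and step 5 shows that every patient at a protocol ALP level is counted. Cholestasis terms also have their own SMQ listing.
- *That bilirubin at Visit 801 is lost for everyone, or that a rise after stopping goes uncounted.* The documents support only a conflict between two sentences, and the lead-in, if it governs, includes Visit 801. Even on the narrow reading a completer's Week 24 draw counts, at 169 - 155 = 14 days after the last dose, and early discontinuers keep visits within the 42-day limit. Follow-up bilirubin also reaches the outputs in step 6.

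It can also be said that the protocol's ALP levels guide the care of individual participants, and nothing obliges the SAP to tabulate them. That stands, and it is why the ALP rows are offered as an addition and not as the correction of an error. Protocol 2.3 is also cautious, speaking only of a possibility.

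What the reply does not remove is the contradiction in the bilirubin window. A patient with bilirubin above the limit at baseline who first reaches 2x ULN at Visit 801 would, on the literal reading, appear in no readable by-arm rate table.

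**Conclusion.** The point holds as a minor reporting inconsistency with a related gap. The bilirubin bullet conflicts with its lead-in and with the three parallel bullets. Followed literally, it removes one scheduled draw of 11 for a completer from the only by-arm table at 2x ULN. The ALP table loses no patients, but the readable plan contains no by-arm rate for ALP severity or for ALP together with bilirubin.

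This rests on three assumptions: visits occur on schedule; the bullet, where it is more specific, might be taken to override the lead-in; and the blacked-out parts of the SAP contain no further hepatic tables. The documents give no expected rate of bilirubin elevation after treatment, so the number of participants affected cannot be stated. The primary efficacy result is unaffected.

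**What to change.** Change the window in the bilirubin bullet from the treatment period to the treatment and follow-up periods, so that it matches the ALT, AST and ALP bullets and agrees with the lead-in. This is one phrase, needs no new data, and should be settled before unblinding.

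As an optional addition, report by arm the numbers with ALP at least 2x ULN, ALP at least 3x ULN, and ALP above 2.5x ULN with bilirubin above 2x ULN. State whether the joint row requires both values in the same sample or uses the maxima, as the eDISH plot does. These rows use levels already in the protocol, for reporting only, and change no clinical rule. The cost is three table rows, which are likely to be sparse.

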6.19.5.4. Lipids Effects

Analyses for the change from baseline to last observation, and shift tables in total cholesterol, LDL cholesterol, HDL cholesterol, and triglycerides are described in Section [6.19.5](#).

TEAEs potentially related to hyperlipidemia will also be analyzed, based on reported AEs. The target surveillance term “Hyperlipidemia” is a Lilly-defined MedDRA search criteria list that is a subset of the PTs in the MedDRA SMQ “Dyslipidemia” that are related to elevated or increased lipids. MedDRA PTs, each with a narrow scope from the SMQ, for the target surveillance term are shown in [Appendix 5](#). Frequency and relative frequency for each PT will be provided, ordered by decreasing frequency in the LY3471851 **CCI** treatment group.

6.19.5.5. Renal Function Effects

Effects on renal function will be assessed through analyses of creatinine, which are described in Section [6.19.5](#).

6.19.5.6. Elevations in Creatine Phosphokinase

Analyses of creatine phosphokinase are described in Section [6.19.5](#).

6.19.6. Vital Signs and Other Physical Findings

Vital signs and physical characteristics include systolic blood pressure, diastolic blood pressure, pulse, weight, body mass index, and body temperature. Original-scale data will be analyzed. When these parameters are analyzed as continuous numerical variables, unplanned measurements will be excluded. When these parameters are analyzed as categorical outcomes, planned and unplanned measurements will be included.

The planned analyses described for the laboratory analytes in Section [6.19.5](#) will be used to analyze the vital signs and physical characteristics.

[Table KFAJ.6.1](#) defines the low and high baseline values as well as the criteria used to define treatment-emergence based on postbaseline values. Postbaseline values include all values after baseline in the treatment and follow-up periods. The blood pressure and pulse rate criteria are consistent with the document *Selected Reference Limits for Blood Pressure, Orthostasis, and ECG Numerical Parameters (Including Heart Rate) for Use in Phase II-IV Clinical Trials Version 1.1* approved on 8 March 2013 as recommended by the Lilly Cardiovascular Safety Advisory Committee.

Table KFAJ.6.1. Categorical Criteria for Abnormal Treatment-Emergent Blood Pressure and Pulse Measurement, and Categorical Criteria for Weight Changes for Adults

Parameter (Units of Measure)	Low	High
Systolic Blood Pressure (mm Hg)	≤90 (low limit) and decrease from lowest value during baseline ≥20 if >90 at each baseline visit	≥140 (high limit) and increase from highest value during baseline ≥20 if <140 at each baseline visit
Diastolic Blood Pressure (mm Hg)	≤50 (low limit) and decrease from lowest value during baseline ≥10 if >50 at each baseline visit	≥90 (high limit) and increase from highest value during baseline ≥10 if <90 at each baseline visit
Pulse (beats per minute)	<50 (low limit) and decrease from lowest value during baseline ≥15 if ≥50 at each baseline visit	>100 (high limit) and increase from highest value during baseline ≥15 if ≤100 at each baseline visit
Weight (kilograms)	(Loss) decrease ≥7% from lowest value during baseline	(Gain) increase ≥7% from highest value during baseline

Abbreviation: mm Hg = millimeters of mercury.

6.19.7. Additional Safety Sections

6.19.7.1. Symptoms of Depression (QIDS-SR16)

The QIDS-SR16 is a 16-item, self-report instrument intended to assess the existence and severity of symptoms of depression as listed in the American Psychiatric Association's *Diagnostic and Statistical Manual of Mental Disorders*, 4th Edition (DSM-IV; APA 1994). Patients are asked to consider each statement as it relates to the way they have felt for the past 7 days. There is a unique 4-point ordinal scale for each item with scores ranging from 0 to 3 reflecting increasing depressive symptoms as the item score increases. Additional information and the QIDS-SR16 questions may be found on the University of Pittsburgh Epidemiology Data Center website (<http://www.ids-qids.org/index.html>). A key reference for this instrument covers its psychometric properties for use in patients with chronic major depression (Rush et al. 2003). Quick Inventory of Depressive Symptomatology was developed at UT Southwestern.

The QIDS-SR16 total score is derived as the sum of the scores across the 9 scale domains. For scale domains that contain more than 1 item, the domain score is the highest item rating given across the items within that domain:

- sleep: the highest score on any 1 of the 4 sleep items (items 1 to 4)
- depressed mood: Item 5
- weight/appetite change: the highest score on any 1 of the 4 weight items (items 6 to 9)
- psychomotor changes: the highest score on either of the 2 psychomotor items (items 15 and 16)
- concentration: item 10
- worthlessness/Guilt: item 11
- suicidal ideation: item 12
- decreased interest: item 13, and
- decreased energy: item 14.

In the presence of missing data, the following rules will be employed to derive the total score. Firstly, considering the 3 multi-item domains (sleep, weight/appetite change, psychomotor changes), the domain score should be based on the maximum value across the appropriate items, and it should be missing only if each item is missing. Further, considering the 9 domain scores, the total score should be derived as missing if there are 3 or more domains that are missing; if 1 or 2 domain scores are missing, then the total score should be derived using a total score that is prorated to the full scale range (0 to 27) based on the available domain scores, retaining 1 decimal place in the total score derived in the presence of missing data.

The QIDS-SR16 total scores will also be categorized in the following severity classes as shown in [Table KFAJ.6.3](#).

Table KFAJ.6.3. QIDS-SR16 Severity of Depressive Symptoms Categories Based on the QIDS-SR16 Total Score

QIDS-SR16 Severity of Depressive Symptoms Category	QIDS-SR16 Total Score
0 = None	0-5
1 = Mild	6-10
2 = Moderate	11-15
3 = Severe	16-20
4 = Very Severe	21-27

Abbreviation: QIDS-SR16 = Quick Inventory of Depressive Symptomatology Self-Rated.

Treatment differences in mean change QIDS-SR16 total score will be analyzed using the MMRM model described in Section 6.2. Only visits that occur on or before the date the patient discontinued treatment will be included in this analysis.

Using the QIDS-SR16 Severity of Depressive Symptoms Categories shown in [Table KFAJ.6.3](#), shift tables will show the number and percentage of patients with total score in each category based on baseline to maximum category during the treatment period and up to 60 days after treatment discontinuation, with baseline depicted by the most extreme category during the baseline period, with further summarization of change from baseline in severity using categories of any improvement, no change, and any worsening, by treatment. Similarly, shift tables will be created for the QIDS-SR16 suicidal ideation item (Item 12) responses.

Treatment-emergent changes in QIDS-SR16 total score severity categories will be characterized as follows:

- Increase (from None) to Mild, Moderate, Severe, or Very Severe
- Increase (from None or Mild) to Moderate, Severe, or Very Severe
- Increase (from None, Mild, or Moderate) to Severe or Very Severe
- Increase (from None, Mild, Moderate, or Severe) to Very Severe

Treatment-emergent changes in QIDS-SR16 suicidal ideation item (Item 12) responses will be characterized as follows:

- Increase (from 0) to 1 to 3
- Increase (from 0 to 1) to 2 to 3, and
- Increase (from 0 to 2) to 3.

